^c Buttocks will be photographed before and after injection site and dimple marking on Days 1, 22, and 43. Buttocks will also be photographed during the Days 2, 4, 7, 14, and 71 visits (ET) (no dimple or injection site markings).

^{d.} Before injection.

^e Subjects will be assigned to 1 of 6 cohorts according to a site specific Mitigation Treatment Assignment Table. Cohort 1 =no mitigation treatment; Cohorts 2-6 = mitigation treatments

^f. Before QWO (CCH-aaes) injection, and 5 and 15 minutes after injection.

^g Using mirrors, or photographs captured either by the subject or another person with the subject's imaging device (ie, cell phone, digital camera), or images captured by the investigator or designee using the site's digital photography system.

^h Baseline Hexsel CSS Subsection D must be '0' (absence of flaccidity or sagging skin) or '1' (slightly draped appearance) on each buttock.

ⁱ Baseline CR-PCSS rating must be a '3' (moderate) on each buttock.

^j Based on live assessments while the subject is in front of the investigator.

^k Compression garments will be worn after QWO (CCH-aaes) injection on Day 1 and worn 24 hours a day for the next 7 days.

Apply instant cold packs immediately after QWO (CCH-aaes) injection for 5-10 minutes immediately after CCH-aaes injection while subject is in a prone position.

^m Arnica patches applied BID for 2 days immediately after QWO (CCH-aaes) injection on Day 1.

- ⁿ Inhance Post-Injection Serum is applied QID directly on and around the injections site for up to 7 days after QWO (CCH-aaes) injection on Day 1, until resolution of bruising.
- PDL treatment between Days 1 (same day of QWO [CCH-aaes) injection) and Day 7 after QWO (CCH-aaes) treatment. PDL settings are according to the investigator's discretion.
- P For the second and third QWO (CCH-aaes) treatment sessions, at the investigator's discretion, subjects will be allowed to use the same mitigation treatment in the same buttock (as applicable) that received mitigation treatment for the first CCH-aaes treatment session.
- ^q AEs will be collected from the time the subject signed the ICF until end of the study or early termination.
- BID = twice daily, d = Days, ET = early termination, ICF = informed consent form, QID = Four times daily

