6. STUDY TREATMENT

Study treatment comprises QWO (CCH-aaes) and mitigation treatments.

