7. DISCONTINUATION FROM STUDY TREATMENT AND STUDY WITHDRAWAL

7.1. Discontinuation of Study Treatment

Subjects who discontinue study treatment (QWO [CCH-aaes], or mitigation treatment) or are withdrawn from the study for any reason, will be encouraged to complete the remaining study visits and evaluations and provide any additional follow-up information as required by the study, unless the subject specifically indicates that they will not participate in any further evaluations. The date of and reason for study treatment discontinuation will be recorded.

Permanent study treatment discontinuation is required for any of the following:

• The subject becomes pregnant during the study.

Subjects who discontinue from study treatment at any time after the first dose of study treatment (QWO [CCH-aaes] and mitigation treatments) will not be replaced.

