7.2. Subject Withdrawal from the Study

Subjects may withdraw from the study at any time at their own request, or may be withdrawn at any time at the discretion of the investigator for safety, behavioral, compliance, or administrative reasons. The date of and reason for withdrawal will be recorded.

If the subject withdraws consent for disclosure of future information, the sponsor may retain and continue to use any data collected before such withdrawal of consent. If a subject withdraws from the study, the subject may request destruction of any samples taken and not tested and the investigator must document this in the site study records.

A subject may be withdrawn from the study for the following medical or administrative reasons:

- Withdrawal by subject (reason must be specified).
- An AE.
- Death.
- A protocol deviation (reason must be specified, for example: lack of compliance, use of a prohibited concomitant medication, etc).
- Lost to follow-up.
- Other reasons (reason must be specified, for example: the subject moved, pregnancy, investigator decision, sponsor decision to terminate the study, etc).

If a subject withdraws from the study, all early termination (ET) procedures should be conducted as detailed in schedule of assessments. The date a subject withdraws and the reason for withdrawal will be recorded in the electronic case report form (eCRF). If, however, a subject withdraws consent, no additional procedures are required except the collection of AE information. This information should be recorded in the source documentation and the eCRF.

Subjects who have been withdrawn from the study at any time after the first dose of study treatment (QWO [CCH-aaes], mitigation treatments) will not be replaced.

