8. STUDY ASSESSMENTS AND PROCEDURES

Study procedures and their timing are summarized in the schedule of assessments (Section 1.3). Adherence to the study design requirements, including those specified in the schedule of assessments, is essential and required for study conduct. Protocol waivers or exemptions are not allowed.

Urgent safety concerns should be discussed with the sponsor immediately upon occurrence or awareness to determine if the subject should continue study treatment and/or be withdrawn from the study.

All screening evaluations must be completed and reviewed to confirm that potential subjects meet all eligibility criteria. The investigator will maintain a screening log to record details of all subjects screened and to confirm eligibility or record reasons for screen failure, as applicable.

Procedures conducted as part of the subject's routine clinical management and obtained before signing of the ICF may be utilized for screening or baseline purposes provided the procedures met the protocol-specified criteria and were performed within the time frame defined in the schedule of assessments.

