8.4. Adverse Events and Serious Adverse Events

The definitions of AEs and SAEs can be found in Section 10.2.

All AEs, including both observed or volunteered problems, complaints, signs or symptoms must be recorded, regardless of whether associated with the use of study treatment. Study treatment includes QWO (CCH-aaes) and mitigation treatments. This would include AEs resulting from
concurrent illness, reactions to concurrent medication use, or progression of disease states (excluding the disease under study). A condition present at baseline that worsens after initiation of study treatment will be captured as an AE; the onset date will be the date the event worsened. The AE should be recorded in standard medical terminology when possible.

8.4.1. Time Period and Frequency for Collecting Adverse Event and Serious Adverse Event Information

All SAEs and AEs will be collected by the investigator from the time of signing the ICF through the Day 71 visit or for 28 days after the last study treatment for those who early terminate. This will include any AEs that are ongoing at the time of completion/termination of the study.

Investigators are not obligated to actively seek AEs and SAEs after conclusion of subject study participation. However, if the investigator learns of any SAE, including death, at any time after the subject has been discharged from the study, and the investigator considers the event to be reasonably related to the study treatment or study participation, the investigator must notify the sponsor within 24 hours as described in Section 10.2.4.1.

All SAEs will be recorded and reported to the sponsor or designee within 24 hours. The investigator will submit any updated SAE data to the sponsor within 24 hours of it being available. The method of recording, evaluating, and assessing causality of AEs and SAEs and the procedures for completing and submitting SAE reports are provided in Section 10.2.

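### Schedule footnote q closes AE collection at early termination, while Protocol 8.4.1 keeps it open until 28 days past the last study treatment

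*Protocol*

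**What the plan says.** **The schedule.** Protocol 1.3, footnote q: "AEs will be collected from the time the subject signed the ICF until end of the study or early termination". The schedule reproduced as SAP Table 2 carries the same footnote.

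**The section on the collection period.** Protocol 8.4.1 has the investigator collect all SAEs and AEs from consent "through the Day 71 visit or for 28 days after the last study treatment for those who early terminate". Protocol Section 6 defines the term: "Study treatment comprises QWO (CCH-aaes) and mitigation treatments".

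**Which text governs.** Protocol Section 8 describes the schedule as a summary of procedures and timing, then adds: "Adherence to the study design requirements, including those specified in the schedule of assessments, is essential and required for study conduct". No precedence rule is given.

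**Related provisions.**
- 8.4.2: subjects are asked at every visit about AEs since the previous one.
- 8.4.3: ongoing AEs are followed to resolution or to 28 days from the last study treatment, whichever is earlier; SAEs are followed until resolved or stable.
- 8.4.1 also covers late SAEs: "if the investigator learns of any SAE, including death, at any time after the subject has been discharged from the study", and considers the event reasonably related, the sponsor must be told within 24 hours.
- 7.2: after withdrawal of consent, "no additional procedures are required except the collection of AE information". No end date is given for that collection.
- SAP 2.11 lists the AE data items without a collection period, and the TEAE definition in SAP 3.5.1 has a start bound but no end bound.

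**The concern.** Two passages address the same people, subjects who terminate early, and give different stopping points. The footnote is what a coordinator is likely to have open when arranging a visit, and the schedule contains nothing after the Day 71/ET column. A site could therefore close the AE record at ET and believe itself compliant, while another site follows 8.4.1 and asks again later. Early leavers would then be observed for different lengths of time depending on the site.

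The percentage of subjects with each AE and TEAE is a secondary endpoint, summarised by cohort. Because the SAP sets no end bound on a TEAE, the analysis would not even out the difference. With 8 subjects per cohort, one additional subject with a given term moves that cohort's percentage by 1/8 = 12.5 points. That happens only if an early leaver has her first occurrence of the term after ET.

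**Working it through.** **Inputs**
- Footnote q end: E, the study day of ET (Protocol 1.3; SAP Table 2).
- 8.4.1 end: L + 28, where L is the day of the last study treatment, QWO or mitigation (Protocol 8.4.1 and 6).
- QWO sessions on Day 1, about Day 22 and about Day 43, the later two with a window of ±3 days (Protocol 1.3).
- Mitigation timing after session 1 (Protocol 6.2.2): cold packs on Day 1; arnica on Days 1–2; garment to Day 8; serum for up to 7 days after injection, so up to Day 8; a single laser treatment on Days 1–7.
- 48 subjects planned, about 45 expected to complete (Protocol 1.1).

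**The plan's own figures.** From the nominal third session to the last visit is 71 − 43 = 28 days, so the 28-day rule matches the planned follow-up of a subject who receives all three sessions. The stated participation also reproduces: 14 screening days + 71 + 7 days of window = 92.

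**Shortfall under the footnote** = (L + 28) − E, for E between L and L + 28.

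- Maximum, ET on the day of the last treatment (E = L): 28 days.
- Zero when ET falls exactly 28 days after the last treatment.

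ET on Day 14, after session 1 with mitigation completed:

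| Cohort | L | L + 28 | Shortfall (days) |
|---|---|---|---|
| 1 (none), 3 (cold packs) | 1 | 29 | 29 − 14 = 15 |
| 4 (arnica) | 2 | 30 | 30 − 14 = 16 |
| 2 (garment) | 8 | 36 | 36 − 14 = 22 |
| 5 (serum) | up to 8 | up to 36 | up to 22 |
| 6 (laser) | 1 to 7 | 29 to 35 | 15 to 21 |

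After a third session on Day 43 with no mitigation that time, ET on Day 44 gives 71 − 44 = 27 and ET on Day 70 gives 71 − 70 = 1. If a garment is worn for 7 days after that session, L = 50, and ET on Day 70 gives 78 − 70 = 8.

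**What is exposed in that interval**

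| Event | Covered if the site stops at ET? |
|---|---|
| AE that began before ET, including one that caused withdrawal | Yes: already recorded, then followed under 8.4.3 |
| New SAE the investigator learns of and considers related | Yes: late-SAE clause of 8.4.1 |
| New SAE not learned of, or judged unrelated | No |
| New non-serious AE | No |

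**Subjects.** 48 − 45 = 3, and 3/48 = 6.25%. This is a planning figure, not a cap. Anyone lost to follow-up yields no data under either rule.

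**The case against.** The best defence is that the footnote is shorthand and that the protocol shows which text it means. Section 8 calls the schedule a summary, 8.4.1 is the section devoted to the collection period, and the 28-day window recurs in 8.4.3 and, for pregnancy, in 8.4.5. Section 8.4.3 speaks of follow-up at later visits or contacts, and the Last Date in Study entry in SAP Table 11 anticipates contact after the final visit about an AE. Most of this stands: 8.4.1 is very probably the intended rule. It does not remove the conflict, because the same paragraph of Section 8 makes adherence to the schedule mandatory and the schedule has no contact after ET.

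Two stronger readings are tempting, and the documents do not support them.

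First, a reader might infer that the conflict also runs in reverse. Under 7.1 a subject who stops treatment "will be encouraged to complete the remaining study visits and evaluations". If her last treatment was Day 1 and she leaves on Day 43 or Day 70, 8.4.1 taken alone ends at Day 29, which is 14 or 41 days before ET. That shows no loss of data. Section 8.4.2 has her asked about AEs at every visit she attends, and 7.2 requires the ET procedures when she withdraws. It therefore gives no reason to add a rule taking the later of the two dates.

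Second, a reader might infer that the events behind withdrawals would be lost. An AE that leads to withdrawal starts before ET, so both rules collect it and 8.4.3 follows it. Only events with onset after ET are at risk.

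**Conclusion.** The inconsistency is real and minor. For subjects who terminate early within 28 days of their last study treatment, footnote q and its SAP copy end AE collection up to 28 days sooner than 8.4.1 requires. The exposed events are new-onset non-serious AEs after ET, and new SAEs that the investigator does not learn of or does not consider related.

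This assumes that a site applies the footnote literally. The documents give no rate of early termination and no rate of first-occurrence events after ET, so the expected number of missed events cannot be estimated. About 3 subjects affected follows only from the planned completion figure; more or fewer is possible. The Day 4 bruising endpoint and the sample size are not affected. For subjects who complete the study, both rules lead in practice to the Day 71 visit.

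**What to change.** Replace footnote q in Protocol 1.3 and in SAP Table 2 with text such as:

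*AEs and SAEs: from ICF signature to the Day 71 visit; in early terminators, until 28 days have passed since the final study treatment (QWO or mitigation), per Section 8.4.1. Any AE reported at an attended visit is still recorded, per Section 8.4.2.*

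Nothing in 8.4.1's rule has to change. How the site makes the contact after ET can be left to it; a prescribed telephone call is more than the contradiction requires.

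**Cost.** One footnote in two documents, in a protocol amendment with IRB approval, and a brief contact after ET for a few early leavers. Some of them may run past 92 days. For example, session 3 on Day 46 followed by 7 garment days gives L = 53; 53 + 28 = Day 81, and with 14 screening days that is 95. Section 8.4.1 as written already implies this, so the participation text could say so. No visit date or endpoint moves.

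**Clerical corrections for the same amendment.** The late-SAE clause in 8.4.1 points to 10.2.4.1 (reporting of AEs); the 24-hour SAE procedure is in 10.2.4.2. Section 8.4.3 points to 10.3 (contraception and pregnancy) for follow-up procedures; it should point to 10.2.

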2. INTRODUCTION

Collagenase clostridium histolyticum (CCH)-aaes (CCH, EN3835, CCH-aaes, QWOTM) is a combination of bacterial collagenases AUX-I and AUX-II, in an approximate 1:1 mass ratio, Collagenase I (Clostridial class I collagenase [AUX-I]) and Collagenase II (Clostridial class II collagenase [AUX-I]). QWO (CCH-aaes) is FDA approved for the treatment of moderate to severe cellulite in the buttocks of adult women.

2.1. Background

The results of the pivotal studies (Studies EN3835-302 and -303) of QWO (CCH-aaes) in edematous fibrosclerotic panniculopathy, otherwise known as cellulite, supported FDA approval of QWO (CCH-aaes) for the treatment of moderate to severe cellulite in the buttocks of adult women. The approved dose of QWO (CCH-aaes) is 0.84 mg per treatment area (buttock) per treatment area for up to 2 treatment areas per treatment session, administered at 3 treatment sessions, approximately 21 days apart. This dose was shown to be an effective treatment of cellulite based on improvement in the severity of cellulite as determined by the investigator and the subject. Overall, the safety profile indicated that QWO (CCH-aaes) was well-tolerated (QWO Prescribing Information). Bruising (injection site bruising) was the most common AE (84%) in the Phase 3 studies. Bruising after the first treatment session was the most robust of the 3 treatment session, with the incidence, duration and severity of bruising decreasing with each subsequent treatment session (Endo Clinical Study Reports EN3835-202, EN3835-205, EN3835-302, EN3835-303).

2.2. Rationale

Although QWO (CCH-aaes)-related post-injection bruising generally resolves within 21 days, and before the next treatment session, bruising is bothersome to subjects due to skin discoloration, and associated swelling and pain. This study will investigate treatments that may mitigate bruising after QWO (CCH-aaes) treatment of cellulite in the buttocks.

Mitigation treatments that may potentially reduce bruising after QWO (CCH-aaes) injection were selected collaboratively with aesthetic physicians based on their experience using mitigation treatments when administering other injectable drugs during aesthetic procedures.

A description of the chemistry, pharmacology, efficacy, and safety of QWO (CCH-aaes) is provided in the QWO Prescribing Information.

2.3. Benefit-Risk Assessment

QWO is approved for the treatment of moderate to severe cellulite in the buttocks of adult women.

The selection of the mitigation treatments and their dose/regimen was a consensus based on the collaborative knowledge and experience of the investigators and Endo, the postulated mechanism of bruising of QWO (CCH-aaes) known to date, and/or supportive literature.

The benefit and risk of each mitigation treatment is described in this section.

2.3.1. Compression Garments

Post-operative compression garments can reduce post-operative bruising, edema, and discomfort (Gladfelter, 2007). Bruising is minimized by compression of small blood vessels and capillaries. Ill-fitting compression garments may cause pain.

2.3.2. Instant Cold Packs

Applying cold (cryotherapy) is commonly used treatment for soft tissue injury (Mayo et al, 2013) and after aesthetic procedures (Brennan, 2014; Verner et al, 2019). Cold induces vasoconstriction and minimizes local cellular damage by restricting hemorrhage (Mayo et al, 2013). It also reduces metabolic demand at the site of injury which aids in healing and recovery.

Mayo et al (2013) compared the effect of bruise reduction treatments of either cold compresses, hydrogen peroxide 3%, an over the counter serum containing vitamin E oil, evening primrose oil, glycerin, and pulse dyle laser (PDL) in 17 patients. There was no significant difference among cold compresses, hydrogen peroxide, and over-the-counter serum in reducing time to bruise resolution.

In a meta-analysis conducted by Lee et al (2017), there was a statistically significant reduction in a cold compress group vs a control group in eyelid ecchymosis after rhinoplasty, at 1 hour and 1 day post-operatively.

Nestor et al (2010) evaluated the use of a cooling device in subjects injected with hyaluronic acid dermal fillers. The use of a cooling system was associated with a mean ecchymosis reduction of 88%, 89%, 80%, and 66% compared to control immediately after injection, at 1 hour, 3 hours, and the day after injection, respectively.

Prolonged application of cold at very low temperatures should be avoided, since this may cause frostbite and nerve injuries (Swenson et al, 1996).

2.3.3. Arnica (OcuMend) Patches

Arnica montana is a perennial of the family Asteraceae. The flowers of its various species contain glycosides, terpinoids, amines, coumarins, and volatile oils (Knackstedt and Gatherwright, 2020). It is purported to have anti-inflammatory and tissue healing actions after trauma bruises or tissue injuries (Ianitti et al, 2016; Widegrow et al, 2020). Various homeopathic oral and topical preparations of different dosages are available. A recent literature review evaluated the efficacy of perioperative arnica in reducing edema, ecchymosis and pain after a variety of aesthetic surgeries including rhinoplasty, blepharoplasty, facial cosmetic surgeries, and laser procedures (Knacksted and Gatherwright, 2020). The data on arnica's effect post-laser treatments was equivocal, however there were differences in technique and application.

Three randomized controlled studies of perioperative oral or topical arnica in rhinoplasty demonstrated decreased ecchymosis (Chaiet and Marcus, 2016; Totonchi and Guyuron, 2007; Simsek et al, 2016). In 2 randomized controlled studies of arnica in upper blepharoplasty, there was no difference in the use of oral (500 mg homeopathic dilution 3 times daily) (Kotlus et al, 2010) or topical arnica (10%) applied twice daily (BID) (van Exsel et al, 2016), compared to placebo.

There were 2 randomized controlled studies that evaluated topical arnica in patients undergoing either 585- or 595-nm laser treatment (Leu et al, 2010; Alonso et al, 2002). In the study

conducted by Leu et al (2010), moderate to severe bruises were induced using a 595-nm variable long-pulsed PDL (spot size 7 mm; fluence 9–11 J; pulse duration 1.5 ms; cooling with 30 ms spray, 20 ms delay with dynamic cooling device). Treatment included either topical arnica 20%, 5% vitamin K, 1% vitamin K and 0.3% retinol, 20% arnica, or white petrolatum applied BID, which was then treated under occlusion BID for 2 weeks. There was less ecchymosis with topical arnica compared to controls and similar results with topical vitamin K. However, results of a study conducted by Alonso et al (2002), found no difference between topical arnica and control. The study evaluated topical arnica (1 × tincture; low homeopathic potency) versus placebo applied BID for either 2 weeks before treatment or 2 weeks after treatment of facial telangiectases. PDL was applied at the settings of 585 nm and a 5 mm spot size was treated with 6.3 J/cm² fluence for all subjects except 1, for whom a 3 mm spot size with a 6.3 J/cm² fluence was used.

In a double-blind placebo-controlled study conducted by Aleshaki and Polich (2020) 18 bruises were mechanically-induced in a single patient by dropping a 3-pound, 2-foot bar of 20 inches onto the skin. Blinded investigators evaluated the extent of bruising after either OcuMend (arnica and ledum palustre patches) or placebo patches were applied. A statistically significant improvement in bruising was observed in the bruises treated with OcuMend compared to placebo. To standardize the strength of arnica and method of application, OcuMend patches will be used in this study.

Use of homeopathic preparations of arnica are generally safe and well tolerated (Ianitti et al, 2016). AEs associated with topical arnica include redness, swelling, and blistering (Leu et al, 2010).

Laser Treatment

Lasers accelerate bruise reduction, by a process known as selective photothermolysis, defined as selectively heating hemoglobin and its breakdown products to accelerate bruise resolution (Mayo et al, 2013; Morton et al, 2013; Verner et al, 2019). PDL, a vascular laser, will be used as a mitigation treatment in this study to reduce bruising after QWO (CCH-aaes) treatment.

The main target chromophore of PDL (585/595 nm) is oxyhemoglobin (absorption peak: 577 nm), which results in its effectiveness in hastening the resolution of ecchymoses. Among its other uses, PDL has been used to treat vascular lesions and post-operative ecchymoses after facial cosmetic procedures (Mayo et al, 2013; Verner et al, 2019).

Defatta et al (2009), used PDL to treat 20 patients with ecchymosis due to facial cosmetic surgeries (ie, cervicofacial rhytidectomy, facial lipocontouring). On post-operative Day 5, half of the bruise was treated. A 10-mm spot size was used, with pulse duration of 6 ms, fluence of 6 J/cm², and cryogen spray for 30 ms with a 20-ms delay for 3 passes. The patients returned 48-72 hours later for PDL of the untreated areas under the same parameters, and had a final follow-up assessment 48 hours after. Photographs of the treated areas were obtained before and after PDL treatment. Ecchymoses captured on the photographs was graded on a scale of 0 to 3 (with a score of 3 indicating severe ecchymosis) by 3 blinded independent observers. PDL treatment resulted in a 63% mean improvement in ecchymosis scores within 48 to 72 hours. The authors indicated that in their experience, maximal efficacy of PDL was observed when it was performed between 5 and 10 days post-operatively.

Karen et al (2010), used PDL to treat 10 patients with ecchymosis due to cosmetic procedures or traumatic injury. Each subject served as his or her own control: subjects with 2 ecchymoses had 1 treated; those with a single lesion had half treated. Photographs were taken before treatment and at 24 hours, 48 hours, and 7 days after treatment. Treated bruises were between 24 and 72 hours old. Subjects received a single treatment with the 595-nm V-Beam PDA (Candela Corp, Wayland, Massachusetts) with the following settings: spot size, 10 mm; fluence, 7.5 J/cm²; and pulse duration, 6 ms. The Dynamic Cooling Device (Candela Corp) was set at 30 ms with a 20 ms delay. Two (2) blinded assessors graded bruise severity from 0 to 10 (0, no bruise; 10, worst bruising). Forty-eight (48) hours after treatment, the average improvement was 76% and 37% for treated and untreated lesions, respectively. One (1) week after treatment, treated and untreated and untreated bruises had improved by 87% and 81%, respectively.

Accelerated resolution of the treated bruise was observed within 24 hours. Twenty-four (24) hours after treatment, the average reduction in the size of the ecchymosis was 62% and 13% for treated and untreated bruises, respectively. Forty-eight (48) hours after treatment, the average improvement was 76% and 37% for treated and untreated lesions, respectively. The authors suggested that the most dramatic response occurred when hemoglobin predominates AEs attributed to PDL treatment include mild discomfort and edema (Defatta et al, 2009), transient crusting (Karen et al, 2010), and redness and bruising when used at higher settings intended to induce bruising (Alonso et al 2002; Leu et al, 2010).

^{2.3.4.} INhance Post-Injection Serum with TriHex Technology[®]

INhance Post-Injection Serum with TriHex Technology is a commercial product containing the following ingredients: Water/Aqua/Eau, Glycerin, Caprylic/Capric Triglyceride, Propanediol, Polyacrylate-13, Lactoferrin, Phosphatidylserine, Palmitoyl Hexapeptide-12, Palmitoyl Tripeptide-1, Hexapeptide-11, Acetyl Hexapeptide-38, Acetyl Tetrapeptide-2, Sodium Hyaluronate Crosspolymer, Tremella Fuciformis Sporocarp (Silver Ear Mushroom) Extract, Peucedanum Graveolens (Dill) Extract, Hydroxymethoxyphenyl Decanone, Dunaliella Salina Extract, Betaine, Ledum Palustre (Labrador Tea) Extract, Arnica Montana Flower Extract, Phospholipids, Xylitylglucoside, Squalane, Caprylyl Glycol, Anhydroxylitol, Polysorbate 20, Xylitol, Butylene Glycol, Sorbitan Isostearate, Ethylhexylglycerin, Caprylhydroxamic Acid, Ascorbyl Palmitate, Xanthan Gum, Pentylene Glycol, Glucose, Helianthus Annuus (Sunflower) Seed Oil, Tocopherol, Potassium Sorbate, Caprylyl Methicone, Polyisobutene, Lecithin, Sodium Hydroxide, Disodium EDTA, Phenoxyethanol.

The effect of INhance Post-Injection Serum vs a moisturizer was evaluated in a randomized, double-blind study of 16 patients who received an induced bruise via mechanical disruption (ie, venipuncture, blood removal and reinjection) (Widegrow et al, 2020). Of the patients treated with INhance Post-Injection Serum, 81% experienced less bruising after their treatment at Days 2 and 3 compared to placebo. AEs were not reported.

